1.6 Selection of Dosage

The radioactivity range (5 to 15 GBq) applied in this study is derived mainly from previous experiences with ¹⁷⁷Lu-DOTATATE [21], although some caution should be applied as it refers to other radiolabelled compounds in other indications. In addition, data from an individual clinical treatment use (see Section 1.4) of ¹⁷⁷Lu-3BP-227 support the dose range selection and is endorsed by the dosimetry studies performed with the IMP in rats and dogs.

In the phase I dose escalation part of this first in human (FIH) study, 5 GBq fractionated into two administrations (2×2.5 GBq) will be used as starting radioactivity. In radiotherapy, fractionation of the cumulative activity is done for safety and tolerability reasons. Based on the biodistribution data obtained in nontumour bearing rats and dogs and consequent allometric calculation for human exposure and taking the most conservative approach, administration of 5 GBq leads to an organ dose of 0.8 Gy for the bone marrow and 1.4 Gy for the kidneys. These organ doses are more than 50% below the organs dose limits of 2 Gy and 23 Gy, respectively. In an individual clinical treatment use (see Section 1.4), four subjects received single administration of 5 GBq without reporting of adverse events (AEs) > Grade 2.

During dose escalation, it is planned to not exceed the cumulative activity of 15 GBq activity (2×7.5 GBq). However, if the MTCA is not reached and if limiting organ dose levels are not exceeded, an additional cohort with three administrations at 7.5 GBq may be added, leading to a cumulative activity of 22.5 GBq. The dosage used in the dose expansion part will be based on the results obtained from the dose escalation part and from the modelling and simulation approach. Similarly, results generated during the dose expansion part will drive the dosage that will be used in phase II. In any case, subjects will be administered with cumulative activities that may be either the MTCA determined in the escalation part or a lower dose with near optimal activity.

In this study, $25 \,\mu g$ (22.1 nmol) of 3BP-227 per 1 GBq ¹⁷⁷Lu will be used. This radioactivity-small-molecule ratio was used in an individual treatment use (see Section 1.4) and yields a specific activity of approximately 45 MBq/nmol, which is routinely achieved with -DOTA-conjugated compounds and is considered clinically acceptable [21, 22].

In Table 2, the safety margins for each species are presented based on the human equivalent dose calculated from body surface area as per Food and Drug Administration (FDA) Guidance for Industry "Estimating the Maximum Safe Starting Dose in Initial Clinical Trials for Therapeutics in Adult Healthy Volunteers" [23]. The small-molecule 3BP-227 has been administered within a nonclinical safety program carried out in rats and dogs following a single administration. The NOAELs determined in the rats and dogs were 2 mg/kg and 1 mg/kg, respectively. Compared to the animal studies, a wide safety margin is observed (based on the most sensitive species, a safety factor margin of more than 300 for the starting dose activity and more than 100 for the targeted maximum radioactivity). At the dose range of 3BP-227 used in this study, no pharmacological effect is expected.

Table 2 Estimated Safety Margin in Study/Species based on Human Equivalent Dose Calculated Based on Body Surface Area

Study	Dose/activity	HED of 3BP-227	Estimated safety margin for 3BP-227 [a]
Study phase I/IIa	Starting dose: 2.5 GBq of ¹⁷⁷ Lu-3BP-227 Corresponding to: • A total of 62.5 μg of 3BP-227 (2.5×25μg) per administration • 1 μg/kg of 3BP-227 per administration Maximal dose: 7.5 GBq of ¹⁷⁷ Lu-3BP-227 Corresponding to: • A total of 187.5 μg of 3BP-227 (7.5×25 μg) per administration • 3.1 μg/kg of 3BP-227 per administration		
Single dose rat Study [contact]	NOAEL (3BP-227)= 2 mg/kg	0.322 mg/kg	Starting dose: 322 times below NOAEL Maximal dose: 104 times below NOAEL
Single dose dog Study [contact]	NOAEL (3BP-227)=1 mg/kg [b]	0.556 mg/kg	Starting dose: 556 times below NOAEL Maximal dose: 179 times below NOAEL

HED=human equivalent dose; NOAEL=no observed adverse events level.

Rationale for use of ¹⁷⁷Lu labelling for Screening Purposes and as a Threshold for Radiodiagnosis

¹⁷⁷Lu is a beta (β)- and gamma (γ)-emitting radionuclide. It is a medium-energy β emitter with a maximum energy of 0.498 MeV and maximum and mean soft-tissue penetration depths of 1.7 mm and 0.23 mm, respectively. The $t_{1/2}$ is 6.7 days (159.5 hours). ¹⁷⁷Lu also emits low-energy γ-rays at 208 and 113 KeV with 11% and 6% relative abundance, respectively, which allows scintigraphy and subsequent dosimetry with the same product. The radiochemical physical characteristics of ¹⁷⁷Lu are described in Table 3 [21].

 177 Lu presents the advantage of emitting just enough γ radiation for quantitative imaging necessary for dosimetry calculation while the β radiation induces the therapeutic effect.

a based on HED and on body surface area (divided by 1.8 for dogs and 6.2 for rats)
 The calculations are based on the following basis: 1 GBq/25 μg 3BP-227 and human body weight of 60 kg

b 2 mg/kg 3BP-227 was tested in study [contact] and was considered within the Maximum Tolerated Dose due to slight transient increase in QT interval. A safety pharmacology study tested 1mg/kg 3BP-227 did not show any adverse cardiovascular effect. The NOAEL of 1 mg/kg 3BP-227 is derived from the combination of these two studies.

For imaging purposes, the γ emission of ^{177}Lu is accompanied by the additional radiation burden of β emission of ^{177}Lu . Therefore, when radiotherapy is not required, the administration of ^{177}Lu may deliver an undesirable radioactivity to the subject. However, the theranostic potential of ^{177}Lu outweighs the above disadvantage particularly in advanced malignant tumours and avoids the uncertainties that may occur from the use of different isotopes with different kinetics that could result in less accurate dosimetry planning.

Physical half-life t½	6.65 days
Decay product	¹⁷⁷ Hf
Maximum β-particle energy	0.498 MeV
Mean β-particle energy	0.133 MeV
Median tissue penetration	0.23 mm
Max. tissue penetration	1.7 mm
Main gamma emission lines	113 keV (6%)
-	208 keV (11%)

Table 3 Radiochemical Physical Characteristics of ¹⁷⁷Lutetium

[figure not shown]
The administration of 1.00±0.1 GBq ¹⁷⁷Lu-3BP-227 is considered adequate to ensure a good uptake at tumour level for dosimetry based on a similar application scheme used by Wild et al. [24] for the evaluation of ¹⁷⁷Lu-DOTA-JR11 and will thus be used in this study for screening purpose, after all other required screening assessments have been completed.

A lower radioactivity administration would lead to longer acquisition time and a poor diagnostic signal (with an increase in signal noise to background ratio) associated with the risk of missing subjects who would be eligible for participation in the study and could benefit from the treatment.

1.7 Population to be Studied

In this FIH study, the subject population enrolled to receive the IMP will be restricted to PDAC, CRC, GC, GIST, squamous-cell carcinoma of head and neck (SCCHN) and ES, which are unresectable, locally advanced or metastatic and expressing NTSR1. Due to the late metastatic or advanced stage of the disease and progression or failure of response to standard-of-care treatments, this subject population is expected to have a reduced life expectancy.

Tumours/metastases expressing NTSR1 will be identified and documented through the lesion uptake of ¹⁷⁷Lu-3BP-227 (at low dose) during the screening period. Subjects who participated in the imaging study, Study D-FR-01087-002, with ¹¹¹In-3BP-227 (also called ¹¹¹In-IPN01087) and who have an uptake of ¹¹¹In-3BP-227 in tumour lesions that is more avid than in the nontumoural surrounding tissue based on whole body imaging (planar scintigraphy), as judged by the investigator, can also be considered for enrolment in this study, provided that they fulfil all other inclusion criteria and do not meet any of the exclusion criteria and were imaged with ¹¹¹In-3BP-227 before the first treatment administration (therapeutic dose) of ¹⁷⁷Lu-3BP-227.

In addition, published data also support these NTSR1 expression profiles in the targeted indications [4, 5, 25, 26, 27]. In the PDAC population, the NTSR1 was found expressed in 73% (8/11) of primary tumours and 63% (14/23) of the metastases. Interestingly, the expression of NTSR1 in the membrane compartment was only observed in tumour tissue (85%; 34/40) and never in normal tissue. In addition, a strong expression of NTSR1 messenger ribonucleic acid (mRNA) was found in 76% (19/25) of the cases of colorectal adenocarcinoma (resection material). Protein overexpression has been documented by immunochemistry in 71% (149/210) of GC samples. For ES, expression of NTSR1 in the membrane compartment has been found in 65% (11/17) of the resection tissue material [6].

The five study populations will be enrolled in the phase I dose escalation part. Based on tumour uptake, safety and preliminary antitumour effect (ORR), the number of study populations might be revised for the potential phase I expansion cohorts and phase II through a protocol amendment.

1.8 Known and Potential Risks to Human Subjects

This is the FIH study conducted with ¹⁷⁷Lu-3BP-227 under controlled conditions. The study will primarily evaluate the safety and tolerability of ¹⁷⁷Lu-3BP-227 but also its potential antitumour effect in subjects with advanced cancers expressing NTSR1. With the exception of an individual clinical treatment use (see Section 1.4), ¹⁷⁷Lu-3BP-227 has never been tested in humans, but has shown no relevant toxicological effects in the animal studies conducted with high safety margins. However, it cannot be ruled out that ¹⁷⁷Lu-3BP-227 could have adverse effects in the human population, which have not been detected in animal studies.

As this is the FIH study, the function of organs identified at risk will be checked as part the of exclusion criteria. Based on the current level of knowledge, those organs are bone marrow, kidney, large intestine, liver and urinary bladder. In conventional fractionated external radiotherapy, the experience is that an absorbed dose of 23 Gy to the kidney gives a 5% expected risk of nephrotoxicity within 5 years [28, 29, 30]. For the bone marrow, a maximum absorbed dose (MAD) of 2 Gy gives approximately a 2% risk of developing leukaemia as a long-term toxicity. In this study, the well-established 2 Gy for the bone marrow MAD and the more conservative approach with 23 Gy as MAD for the kidney will be applied.

Safety measures have been taken into consideration to minimise the risk. Each subject recruited across the sites may be hospitalised for 24 hours following administration for observation at the discretion of the investigator. The level of radioactivity will be monitored until it has fallen to safe levels for discharge, to protect medical personnel and relatives. Depending on the local

regulation, the subject will be hospitalised either in the nuclear medicine or regular oncology ward.

The participating subjects will be closely monitored during the study and during the long-term follow-up period until lost to follow-up, withdrawal of consent, death or a maximum of 5 years, whichever occurs first. Subjects may be withdrawn from the study at any time, if judged to be in their best interest by the investigator or upon the subject's wish. The study will be carried out in specialised clinical centres with nuclear medicine and medical oncology specialists.

An SRC will review the safety and dosimetry data on a continuous basis (see Section 4.2.1.4). Subject-specific dosimetry will be performed on a regular basis for up to 96 hours after each administration to describe the uptake by the tumour and organs identified at risk over the entire course of treatment. The cumulative organ doses of kidney, bone marrow and liver will be monitored on an ongoing basis as for the other organs identified at risk. If a previous cumulative radioactive dose indicates that the organ limit will be exceeded with the next cycle, the activity of the next cycle will be reduced.

Detailed criteria, based on the percentage of subjects experiencing dose limiting toxicities (DLTs), have been carefully defined to provide guidance on the next radioactive dose selection. The risks associated with this study are considered adequately elucidated and controlled well

by planned cautionary measures in the study design and the target population as well as with the potential benefit of the treatment.

2 STUDY HYPOTHESIS

The present study consists of two parts that aim to test the following hypotheses:

2.1 Phase I

¹⁷⁷Lu-3BP-227 is sufficiently well-tolerated to permit clinical investigation in phase II.

2.2 Phase II

¹⁷⁷Lu-3BP-227 yields higher objective response rates in subjects who have NTSR1 expressing cancers that are unresectable, locally advanced or metastatic based on RECIST version 1.1 by central review and as compared with the historical ORR obtained by current standard-of-care treatment for each tumour type.

3 STUDY OBJECTIVES

3.1 Primary Objectives

3.1.1 Phase I

To establish the safety and tolerability of fractionated i.v. administrations of ¹⁷⁷Lu-3BP-227 in subjects with unresectable, locally advanced or metastatic cancers expressing NTSR1.

3.1.2 Phase II

To estimate ORR of fractionated i.v. administrations of ¹⁷⁷Lu-3BP-227 in subjects with unresectable, locally advanced or metastatic cancers expressing NTSR1.

3.2 Secondary Objectives

3.2.1 Phase I

- (a) To determine the whole-body distribution of ¹⁷⁷Lu-3BP-227 and PK of both ¹⁷⁷Lu-3BP-227 and 3BP-227.
- (b) To determine the radiation dosimetry of ¹⁷⁷Lu-3BP-227 (organ exposure to radiation).
- (c) To describe the preliminary antitumour activity of ¹⁷⁷Lu-3BP-227.

3.2.2 *Phase II*

- (a) To further evaluate the safety profile of ¹⁷⁷Lu-3BP-227 at the radioactivity recommended by the phase I results.
- (b) To further assess the response to treatment with ¹⁷⁷Lu-3BP-227 using RECIST version 1.1 and/or PERCIST version 1.0 criteria.
- (c) To further characterise the whole-body distribution and dosimetry of ¹⁷⁷Lu-3BP-227 and PK of both ¹⁷⁷Lu-3BP-227 and 3BP-227.
- (d) To describe the influence of ¹⁷⁷Lu-3BP-227 on the health-related quality of life of treated subjects.

3.3 Exploratory Objectives

3.3.1 *Phase I/II*

- (a) To explore the correlation between the tumour uptake of ¹⁷⁷Lu-3BP-227 and the NTSR1 expression on tumours.
- (b) To explore renal safety by measuring urinary specific biomarkers.
- (c) To evaluate the tumour microenvironment, transcriptomics and other markers of interest for the disease through assessment of tumour biopsies.
- (d) To explore genomic alterations in circulating cell-free DNA (cfDNA) and in germline DNA.
- (e) To collect gene mutation status for correlation with clinical outcome.
- (f) To collect biobank samples for future analysis of circulating markers (optional; additional informed consent required).
- (g) To generate a model integrating PK, dosimetry, antitumour activity and safety data.

4 INVESTIGATIONAL PLAN

4.1 Overall Study Design and Plan

This is a multicentre, open-label phase I/II study of ¹⁷⁷Lu-3BP-227 in subjects with unresectable, locally advanced or metastatic solid tumours expressing NTSR1 who have progressed after their available standard-of-care treatment options and/or are deemed suitable for the treatment with ¹⁷⁷Lu-3BP-227 as per the investigator's clinical assessment and/or their

individual disease state. The study consists of a phase I dose-escalation (and potential expansion cohorts) and a phase II assessing the efficacy of ¹⁷⁷Lu-3BP-227 in subjects with unresectable, locally advanced or metastatic solid tumours expressing NTSR1.

4.2 Phase I

4.2.1 Dose Escalation

Phase I will consist of a radioactivity escalation part with the objective of determining the MTCA. For phase I, subjects enrolled will have unresectable, locally advanced or metastatic tumours expressing NTSR1 originating from either the pancreas (PDAC), colon and rectum (CRC), stomach (GC), gastrointestinal stromal tumours (GIST), head and neck region (SCCHN) or bone (ES).

The study screening period includes a screening administration of ¹⁷⁷Lu-3BP-227 to assess the tumour uptake of each subject by whole body scan (planar scintigraphy, 1 or 2 timepoint(s) at the investigator's discretion) and optional single photon emission computed tomography (SPECT)/CT scans (up to 2 at the investigator's discretion). Only subjects with a tumour uptake higher than nontumoural surrounding tissue (based on investigator's decision) will be deemed eligible for treatment. The screening period will last 3 weeks but can be extended by up to 2 weeks if this is required for logistical reasons. Subjects who participated in the imaging study, Study D-FR-01087-002, with ¹¹¹In-3BP-227 (also called ¹¹¹In-IPN01087) and who have an uptake of ¹¹¹In-3BP-227 in tumour lesions that is more avid than in the nontumoural surrounding tissue based on whole body imaging (planar scintigraphy), as judged by the investigator, can also be considered for enrolment in this study, provided that they fulfil all other inclusion criteria and do not meet any of the exclusion criteria and were imaged with ¹¹¹In-3BP-227 before the first treatment administration (therapeutic dose) of ¹⁷⁷Lu-3BP-227.

During the treatment phase, it is planned that each subject will receive ¹⁷⁷Lu-3BP-227 fractionated into two i.v. administrations separated by 4 to 5 weeks (+4 weeks in case of reversible AEs) (Figure 1). The safety evaluation will be done over 4 weeks between Cycle 1 and Cycle 2 and over 6 weeks between Cycle 2 and end of core trial (EOCT). During this period, subjects will have repeated imaging for the calculation of individual dosimetry data and will be monitored for signs of toxicity.

Tumour response will be assessed on CT or MRI, as well as with ¹⁸F-FDG-PET scans at the EOCT visit, (corresponding to 6 weeks after the second administration).

Subjects may receive up to four additional administrations of ¹⁷⁷Lu-3BP-227 after the EOCT, if they have clinical benefit and an acceptable tolerability profile and if the organ dose limits are not exceeded. The safety data evaluation will be conducted by the sponsor. The decision to administer additional cycles is based on the investigator's judgement and subject's discretion and must be discussed with and agreed upon by the sponsor. The clinical benefit will be defined as complete responder (CR), partial responder (PR) or stable disease or based on their biochemical response.

A long-term follow-up period will start after the EOCT, early discontinuation (ED) or end of additional cycles (EOAC) visit and subjects will be followed up every 3 months (±2 weeks) until lost to follow-up, withdrawal of consent, death or a maximum of 5 years, whichever occurs first.

[figure not shown]

Figure 1 Phase I Study Design Scheme

Note: Population screened includes subjects with unresectable disease.

¹Additional cycles are optional depending on the clinical benefit observed in the subjects during the core trial, as well as on the toxicities and organ absorbed doses.

4.2.1.1 Definition of the MTCA

Several radioactivity amounts of ¹⁷⁷Lu-3BP-227 are planned to be tested according to an adaptive radioactivity escalation plan. Each subject will only participate in one part of the protocol. The purpose of the radioactivity escalation part is to determine the MTCA. If not feasible, the maximum tolerated single activity (MTSA) or the maximum administered cumulative activity (MACA) will be determined according to the situation below:

- The MTCA is defined as the maximum tolerated cumulative activity that may be administered following fractionated i.v. administrations of at least 4 weeks apart, so that:
 - No more than 33% of the subjects experience a DLT during Cycles 1 and/or 2 (see DLT definition in Section 4.7.1.1), and
 - The cumulative radiation in each target organ does not exceed the acceptability limits (see Section 4.7.1).
- The MTSA is defined as the highest single radioactivity that can be given so that no more than 33% of the subjects experience a DLT during Cycle 1. The MTSA will be determined in case of unacceptable toxicity seen after Cycle 1.
- The MACA will be determined if the MTCA is not reached during the dose escalation part.

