4.2.1.3 Dose Escalation Mode

Dose escalation is planned to proceed in two steps, with two different increments for the radioactivity escalation. In the first step, in order to minimise the number of subjects receiving subtherapeutic activity, the inter-cohort radioactivity escalation will be performed by increment of 3 GBq (1.5 GBq per administration), up to the first study drug related treatment-emergent AE (TEAE) (Grade 2 or higher, except hair loss) or until a DLT occurs. Afterwards, the maximum increment will be reduced to 2 GBq (1 GBq per cycle) for all subsequent cohorts if dose escalation is allowed. However, even if no Grade 2 or higher AE are observed up to a cumulative activity of 11 GBq, radioactivity will be increased by 2 GBq (1 GBq per cycle).

Table 5 illustrates the escalation plan based on the escalation scheme defined above. However, if DLTs are reported, a statistical Bayesian modelling approach will be implemented to produce a more precise dose-DLT curve to guide the dose selection (see details in Attachment 5, Section 19.5) and predict an activity not exceeding the MTCA/MTSA that could be tested in the next cohort.

Planned radioactivity Cohort 1 Cohort 2 Cohort 3 Cohort 4 Cohort 5 escalation Cumulative 5 GBq 8 GBq 11 GBq 13 GBq 15 GBq 2.5 GBq/C 4 GBq/C 5.5 GBq/C 6.5 GBq/C 7.5 GBq/C Per cycle

Table 5 Cohorts and Radioactivity Escalation Plan

C=cycle; GBq=gigabecquerel.

Once the dose escalation has been completed, the MTCA level may be repeated in a last cohort (see Section 4.2.1.4 for stopping rules and Section 4.2.1.1 for MTCA definition). If the MTCA is not reached and if limiting organ dose levels are not exceeded at the highest planned activity (2×7.5 GBq) and if no individual withdrawal criteria are met, an additional cohort (Cohort 6) with three administrations at the highest single administration level may be added (3×7.5 GBq).

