4.4 Study Endpoints

4.4.1 Primary Endpoint

4.4.1.1 Phase I

For the dose escalation, the primary endpoint is MTCA or MACA, if the MTCA is not identified during the dose escalation part. The primary variables used for the MTCA determination will be the incidence of DLTs (as defined in Section 4.7.1.1) and the organ exposure to radiation during two cycles of treatment. The DLT period for the determination of the primary endpoint

starts at the first administration of ¹⁷⁷Lu-3BP-227 to EOCT/ED. Safety evaluation will encompass DLTs, frequency and nature of AEs, abnormal findings from physical examination, vital signs, 12-lead electrocardiogram (ECG), 3-lead ECG Holter, Eastern Cooperative Oncology Group (ECOG) performance status deterioration, clinical laboratory tests (including haematology, blood biochemistry, hormone analysis, urinalysis and pregnancy test) and changes in specific renal safety biomarkers.

In case the phase I dose expansion cohorts are implemented, the primary endpoint will be safety and tolerability measured by the type, severity, expectedness and frequency of AEs.

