4.5 Study Duration

For phase I, the maximum duration of subject participation in the core trial is 21 weeks. However, if, according to the investigator, a subject has clinical benefit, the subject may receive up to four additional cycles after the EOCT, provided they have an acceptable tolerability profile and the organ dose limits are not exceeded. This is at the subject's discretion and must be discussed and agreed upon with the sponsor. The clinical benefit will be defined as CR, PR or stable disease (SD) as per RECIST criteria version 1.1 or based on biochemical responses.

For phase I dose expansion and phase II, the study duration will be refined in light of phase I results and recommended treatment regimen (doses and intervals).

In all cases, a long-term follow-up period will start after the EOCT, ED or EOAC visit and subjects will be followed up every three months (±2 weeks) until lost to follow-up, withdrawal of consent, death or a maximum of 5 years, whichever occurs first.

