4.7.1.3 Replacement Rules

In phase I, a cohort will be considered as completed once three subjects of the cohort complete Cycle 2 or discontinue early during Cycle 2 (except for Cohort 1). Except for Cohort 1, if subjects discontinue for any reason other than a DLT (e.g. disease progression) before end of Cycle 2, they may be replaced.

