6.2.2.1 Early Discontinuation or End of Core Trial Visit

Subjects who complete the core trial, i.e. subjects who receive two treatment administrations and who continue the study until 6 weeks after the second dose administration, will be considered as having completed the study.

Subjects who discontinue the study prior to the EOCT visit are considered as early discontinued subjects. The assessments required at the ED visit are the same as the assessments required at the EOCT visit.

Subjects with ongoing AEs or clinically significant laboratory test abnormalities (as determined by the investigator) will be monitored by the investigator as described in Section 4.7.1.

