12.1 Analysis Sets

For dose escalation only, all subjects who complete Cycle 2 or discontinue during Cycle 1 or Cycle 2 due to a DLT will be included in the MTCA and MTSA evaluations.

For the overall study, all subjects who received at least one dose of the IMP will be included in the safety evaluation. All subjects who receive at least one dose of IMP and who have postbaseline efficacy data will be included in the efficacy evaluations. All subjects with evaluable 3BP-227 PK data and no major protocol deviation with an impact on PK analysis will be included in the evaluation of 3BP-227 PK. All subjects with evaluable dosimetry images and no major protocol deviation with an impact on dosimetry analysis will be included in the evaluation of dosimetry. All subjects with evaluable blood or urine dosimetry data and no major protocol deviation with an impact on ¹⁷⁷Lu-3BP-227 PK analysis will be included in the evaluation of ¹⁷⁷Lu-3BP-227 PK. Major deviations will be described in a specific document.

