A TEAE for the long-term follow-up period is defined as any AE that occurs during the long-term follow-up period of the study if:

- It was not present prior to EOCT/ED visit or EOAC/ED visit, or
- It was present prior to EOCT/ED visit or EOAC/ED visit but the grade increased between EOCT/ED visit or EOAC/ED visit and end of study,
- It was present prior to EOCT/ED visit or EOAC/ED visit, the grade is the same but the causality changed to “related” between EOCT/ED visit or EOAC/ED visit and end of study.

In addition, adverse events will be assigned to a specific cycle of treatment for core trial and additional cycles. This assignment will be based on the start date of the adverse event: if the AE start date is on or after the date of treatment X and before the date of treatment X+1 (or if the subject does not receive a treatment X+1 or the treatment X+1 date is missing), then the TEAE will be assigned to Treatment Cycle X.

An overall summary table of all AEs will be presented by treatment group and overall, by cycle (if applicable) and overall, after IMP screening administration, for core trial, additional cycles and follow-up long term separately. In addition, an overall summary table will be presented by pooling cycles from core trial and additional cycles.

TEAEs will be summarised by treatment group and overall with the number and percentage of subjects with AEs classified by primary system organ class and preferred term, by cycle (if applicable) and overall, after IMP screening administration, for core trial, additional cycles and follow-up long term separately. The number of occurrences of a TEAE will also be presented.

In addition, summary tables will also be presented for related TEAEs, SAEs, related SAEs, non-serious TEAEs, TEAEs by decreasing frequency, TEAEs by NCI-CTCAE worst grade (for NCI-CTCAE worst grade  $\geq 3$ ) and TEAEs by most serious causality (category related only).

Summary of TEAEs and related TEAEs will be also summarised by pooling cycles from core trial and additional cycles.

DLTs during cycle 1 or 2 (i.e. occurring between the first administration of Lu-3BP-227 and EOCT/ED) will be summarised by treatment group and overall with the number and percentage of subjects with DLTs classified by primary system organ class and preferred term. The number of occurrences of a DLT will also be presented.

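### The MTCA criterion, evaluable set, EOCT date and DLT and dosimetry summaries are written for two administrations and are not reconciled with the optional three-administration Cohort 6

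*Protocol*

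**What the plan says.** Protocol Section 4.2.1.3 states that, if the MTCA is not reached at 2×7.5 GBq and other conditions hold, "an additional cohort (Cohort 6) with three administrations at the highest single administration level may be added". The protocol synopsis and SAP Section 1.2 give the resulting cumulative activity as 22.5 GBq. Footnote v to Table 8 (repeated in SAP Table 1) is attached to the core-trial header and gives a third cycle the same assessments as Cycle 2.

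The rules that turn data into the primary endpoint refer to two cycles:

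- **MTCA criterion (4.2.1.1):** "No more than 33% of the subjects experience a DLT during Cycles 1 and/or 2".
- **Primary variables (4.4.1.1):** DLT incidence and organ "exposure to radiation during two cycles of treatment".
- **Cohort completion (4.2.1.2, 4.7.1.3):** "a cohort will be considered as completed once three subjects of the cohort complete Cycle 2 or discontinue early during Cycle 2". Replacement applies before the end of Cycle 2.
- **Core-trial completers (6.2.2.1):** "subjects who receive two treatment administrations and who continue the study until 6 weeks after the second dose administration". The synopsis and Sections 4.2.1 and 4.4.2.1 also place EOCT 6 weeks after the second dose.
- **Duration (4.5):** "the maximum duration of subject participation in the core trial is 21 weeks".
- **MTCA/MTSA set (12.1):** "all subjects who complete Cycle 2 or discontinue during Cycle 1 or Cycle 2 due to a DLT".
- **Analysis (12.2.4, 19.5.1):** DLTs in Cycles 1 or 2, modelled on two doses d1 and d2, with the MTCA defined as d1+d2 where d1=d2.
- **SAP 3.2.1.1:** "DLTs during cycle 1 or 2 (i.e. occurring between the first administration of" the product and EOCT/ED). SAP 3.1.3.3 and 3.2.19.7 limit cumulative absorbed dose in the core trial to Cycles 1 and 2.

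None of these passages makes an exception for Cohort 6.

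**The concern.** Cohort 6 would be opened to learn about a third administration. Its first two doses, 2×7.5 GBq, repeat Cohort 5. If the 33% criterion is applied as worded, the rate that defines the MTCA uses only the exposure already studied and omits the new 7.5 GBq, which is one third of the 22.5 GBq.

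The denominator has a matching gap. A subject who completes Cycle 2 and never receives the third dose is evaluable under Section 12.1 and would count as a subject of the 22.5 GBq cohort.

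This matters because the MTCA is the primary endpoint, and Sections 4.3 and 7.1.4.3 make it the ceiling for phase II activity. If the MTCA is not identified, the endpoint becomes the MACA, for which Section 4.2.1.1 gives no DLT criterion. In either case the plan does not say how toxicity after the third dose enters the primary result.

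**Working it through.** **1. The 21-week core trial fits two administrations only.** Inputs: screening of 3 weeks plus up to 2 (Section 4.2.1); the Day 29 window of +7 days, and +28 for toxicity (Table 8); EOCT at Day 43, +7 days (Table 8).

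- Screening: 3 + 2 = 5 weeks.
- One inter-dose cycle at maximum: (28 + 7 + 28)/7 = 9 weeks.
- Last dose to EOCT: (42 + 7)/7 = 7 weeks.
- Two doses: 5 + 9 + 7 = 21 weeks, which is the stated figure.
- Three doses: 5 + 9 + 9 + 7 = 30 weeks.

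Without delays or windows the totals are 3 + 4 + 6 = 13 weeks and 3 + 4 + 4 + 6 = 17 weeks.

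**2. Days after the third dose that fall in the DLT period, with EOCT taken literally as 42 days after the second dose.**

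| Third dose given (days after second) | Days covered after third dose |
|---|---|
| 28 | 42 − 28 = 14 |
| 35 (+7 window) | 42 − 35 = 7 |
| 63 (+7 and +28) | 42 − 63 = −21, so none |

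Using the full +7-day EOCT window adds 7 days: 21 days in the first row, and still none in the last.

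If footnote v is read instead as moving EOCT to after Cycle 3, about 6 weeks after the third dose are covered. The events then qualify as DLTs under Section 4.7.1.1, but the criterion in 4.2.1.1 and the model in 19.5.1 still have no place for them.

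**3. How far a two-cycle rate can understate a three-cycle rate.** The documents give no DLT rate for a third cycle, so this is an illustration. Assume the risk is equal and independent in each cycle. With r the rate through Cycle 2, the per-cycle risk is q = 1 − √(1 − r), and the rate through Cycle 3 is 1 − (1 − q)³ = 1 − (1 − r)^1.5.

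| Through Cycle 2 | Through Cycle 3 | P(≥2 DLTs in 5), two cycles | P(≥2 DLTs in 5), three cycles |
|---|---|---|---|
| 10% | 14.6% | 8% | 16% |
| 15% | 21.6% | 17% | 30% |
| 20% | 28.5% | 26% | 44% |
| 25% | 35.1% | 37% | 57% |
| 33% | 45.2% | 53% | 75% |

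The three-cycle rate reaches 33% when (1 − r)^1.5 = 0.67, that is r = 1 − 0.67^(2/3) ≈ 23%. Under this assumption, a true two-cycle rate between about 23% and 33% meets the criterion as worded while the three-administration rate exceeds 33%.

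**4. Model range.** The logistic model in 19.5.1 has terms for d1 and d2 only. The simulations assumed acceptable organ exposure up to 15 GBq (2×7.5). A dose of 3×7.5 GBq cannot be entered, so the model gives no estimate for Cohort 6.

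**The case against.** A reader might infer that DLTs after the third dose are simply excluded from the primary endpoint. The documents do not settle that:

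- Sections 4.4.1.1 and 4.7.1.1 run the DLT period from first administration to EOCT/ED without naming a cycle.
- Footnote v places the third cycle inside the core trial.
- SAP 3.2.1.1 explains its cycle 1 or 2 wording as the period up to EOCT/ED. It also tabulates subjects with a DLT or Grade ≥2 event by cycle and overall, and lists all DLTs.
- A subject with a Cycle 3 DLT has completed Cycle 2 and so stays in the Section 12.1 set.

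A reader might also infer that organ dose or safety after the third administration goes unmonitored. That is not supported either. The organ-dose part of the MTCA definition and the cumulative limits in Section 4.7.1 have no cycle limit, treatment stops on a DLT or an exceeded limit, and the SRC reviews all cumulative data (12.2.8). The SAP's per-cycle dosimetry summaries are not capped at Cycle 2.

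Finally, Cohort 6 is optional, no later cohort is planned after it, the two-dose model cannot itself return a three-dose MTCA, and phase II needs an amendment.

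All of this stands, and it limits the point to endpoint wording. It does not remove it. On the reading most favourable to the plan, a third-dose event is a DLT by definition yet lies outside the rate that defines the MTCA. The SAP's equation of cycle 1 or 2 with the period to EOCT/ED also fails for a three-cycle cohort.

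**Conclusion.** The passages conflict, or are silent, on how a three-administration cohort contributes to the primary endpoint. Followed literally, the MTCA rate for Cohort 6 would rest on exposure that repeats Cohort 5, and subjects without a third dose would count as evaluable. The documents do not support the stronger statement that third-dose DLTs never count, nor that safety review is missing.

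The schedule figures (21 weeks against 30, and at most 14 days after the third dose without the EOCT visit window) follow from the protocol's own windows, the second of them only if EOCT is read literally. The 15-45% range rests on the assumption of equal, independent per-cycle risk and is an illustration, not a forecast. The gap concerns one optional cohort and leaves Cohorts 1 to 5 untouched. It should be fixed before Cohort 6 opens.

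**What to change.** Before Cohort 6 opens, reconcile the protocol synopsis, Sections 4.2.1, 4.2.1.1, 4.2.1.2, 4.4.1.1, 4.4.2.1, 4.5, 4.7.1.3, 6.2.2.1, 12.1 and 12.2.4, and SAP Sections 3.1.3.3, 3.2.1.1 and 3.2.19.7, with Section 4.2.1.3 and footnote v to Table 8:

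- Make the DLT numerator, the evaluable set and the cumulative organ-dose summary used for the primary endpoint cover every planned core administration in a three-administration cohort.
- State that the d1/d2 model does not cover that cohort.
- Make the EOCT, cohort-completion and duration passages agree with footnote v. How they are made to agree is for the sponsor; no dose, schedule or clinical rule is proposed here.

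The cost is wording in one protocol amendment and the SAP. No additional subjects are needed, and footnote v already schedules the third-cycle visits.
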